8.2 Statistical analysis of the primary efficacy endpoint

The primary efficacy endpoint is the change from Baseline in MG-ADL score to Day 43 (Visit 10) and will be evaluated under the ‘hypothetical & treatment policy’ estimand based on RS using Hypothetical & Treatment Policy strategy.

Missing data in the primary analysis will be handled under a missing at random (MAR) assumption.

To check the assumptions around the estimand in the (primary) analysis of the primary endpoint, the following sensitivity and supplemental analyses will be performed:

- A sensitivity analysis using:
 - Hypothetical & treatment policy strategy on FAS;
 - Hypothetical & treatment policy strategy with a J2R approach on missing data will be used to verify the robustness of the MAR approach;
 - Hypothetical & treatment policy strategy based on the subgroup of the RS who received all [REDACTED] doses.
 - Hypothetical & treatment policy strategy based on the subgroup of the FAS excluding confirmed COVID-19 cases.
- A supplemental analysis using:
 - Composite strategy to handle the occurrence of an intercurrent event as treatment failures. A trimmed mean approach will be implemented to impute missing data;
 - Treatment policy strategy to allow intercurrent events to be included in the treatment paradigm.

An additional analysis will be performed using COVID-19 Hypothetical strategy on RS.

The methods to handle the missing data caused by occurrence of ICEs in each analysis are detailed in [Section 4.2.1](#).

Please see below for details about the estimands attributes for the evaluation of the primary endpoint (primary, sensitivity and supplemental analyses).

1. Treatment Conditions: please see table below.

Table 8-1: Treatment Conditions:

Study Treatment Name:	Rozanolixizumab (Treatment Arm 1)	Rozanolixizumab (Treatment Arm 2)	Placebo (Treatment Arm 3)
Dosage formulation:	Solution for infusion	Solution for infusion	Aqueous solution
Unit dose strength(s)/Dosage level(s):	[REDACTED]		0.9% sodium chloride aqueous solution (physiological saline, preservative free)
Route of Administration	Subcutaneous (sc)		
Dosing instructions:	
█ doses of rozanolixizumab at █ (equivalent to approximately █):
 
Bodyweight <50kg: dose to be administered █
 
Bodyweight ≥50kg and <70kg: dose to be administered █
 
Bodyweight ≥70kg and <100kg: dose to be administered █
 
Bodyweight ≥100kg: dose to be administered █
	
█ doses of rozanolixizumab at █ (equivalent to approximately █):
 
Bodyweight <50kg: dose to be administered █
 
Bodyweight ≥50kg and <70kg: dose to be administered █
 
Bodyweight ≥70kg and <100kg: dose to be administered █
 
Bodyweight ≥100kg: dose to be administered █
	
█ doses of placebo at █

Packaging and Labeling	Rozanolixizumab and matching placebo are manufactured, packaged, and labeled according to Good Manufacturing Practice guidelines and applicable laws or regulations.		

2. **Population:** study participants with generalized MG who comply with the inclusion/exclusion criteria specified in Section 5 in the study protocol
3. **Endpoint:** please refer to Section 2.2.1.1 for details.
4. **Intercurrent Events (ICEs):** See Section 4.2.1.
5. **Population Level Summary (PLS):** See table below.

Table 8-2: Intercurrent Events and Population Level Summary by Statistical Category

Statistical Category	Intercurrent Event Strategy	Population Level Summary
Primary	The ICEs are detailed in Section 8.1 . A hypothetical & treatment policy strategy will be used to handle the ICEs.	Difference in mean change from Baseline (LSMD from CfB MMRM) to Day 43 (Visit 10) in the MG-ADL score for study participants receiving rozanolixizumab versus placebo, using the RS.
Sensitivity	Hypothetical & treatment policy strategy , same as for the primary analysis	Difference in mean change from Baseline (LSMD from CfB MMRM) to Day 43 (Visit 10) in the MG-ADL score for study participants receiving rozanolixizumab versus placebo, using the FAS.
Sensitivity	Hypothetical & treatment policy strategy , same as for the primary analysis	Difference in mean change from Baseline (LSMD from CfB MMRM) to Day 43 (Visit 10) in the MG-ADL score for study participants receiving rozanolixizumab versus placebo, using the RS. A Jump-to-reference multiple imputation approach will be utilised to assess the validity of the MAR assumption. Missing data across all treatment groups will be imputed using the placebo distribution.
Sensitivity	Hypothetical & treatment policy strategy , same as for the primary analysis.	Difference in mean change from Baseline (LSMD from CfB MMRM) to Day 43 (Visit 10) in the MG-ADL score for study participants receiving all [REDACTED] doses of rozanolixizumab versus placebo.
Sensitivity	Hypothetical & treatment policy strategy , same as for the primary analysis.	Difference in mean change from Baseline (LSMD from CfB MMRM) to Day 43 (Visit 10) in the MG-ADL score on the subgroup of the FAS excluding confirmed COVID-19 cases.

Statistical Category	Intercurrent Event Strategy	Population Level Summary
Supplemental	The ICEs are detailed in Section 8.1 . A composite strategy will be used to handle the ICEs.	Difference in mean change from Baseline (LSMD from ANCOVA) to Day 43 (Visit 10) in the MG-ADL score for study participants receiving rozanolixizumab versus placebo. A trimmed mean approach will be used where all missing data (including the main intercurrent events) will be imputed with the worst score of its respected questionnaire. A permutation-based test will be carried out, with the % trimming applied adaptively. The mean treatment difference of the trimmed population will be calculated on covariate-adjusted scores which are derived from an ANCOVA analysis of completers data.
Supplemental	The ICEs are detailed in Section 8.1 . A treatment policy strategy will be used to handle the ICEs.	Difference in mean change from Baseline (LSMD from MMRM) to Day 43 (Visit 10) in the MG-ADL score for study participants receiving rozanolixizumab versus placebo.

Note: CfB=Change from Baseline; LSMD=Least Squares Mean Difference; MMRM=mixed model for repeated measures; ANCOVA= analysis of covariance; MAR=Missing at Random

8.2.1 Derivation of primary efficacy endpoint

The complete list of MG-ADL items and scores are provided in [Table 13–3](#). The total score will be calculated according to the rules set down in [Section 13.3](#). The total score calculated after single item imputation will be used to calculate change from Baseline, in summaries and for efficacy analyses.

8.2.2 Primary analysis of the primary efficacy endpoint

The primary analysis is based on the RS under the hypothetical & treatment policy strategy (see details in [Section 8.1](#)). Any missing MG-ADL scores (including missing data after the intercurrent events) will be handled based on maximum likelihood estimation method under MAR assumption.

A stage-wise MMRM with treatment group, Baseline MG-ADL score, region, stratification factor(s) including MuSK(+/-) and /or AChR(+/-), and treatment group by day (interaction term) as fixed factors and study participant as a random effect. The MMRM will include Days 8, 15, 22, 29, 36 and 43.

The model will utilize an unstructured covariance pattern for the repeated measures. If the model does not converge using the unstructured pattern, then an autoregressive covariance structure

will be used. The Kenward-Roger approximation will be used to estimate the denominator degrees of freedom.

For each stage, the least squares means (LSMs) of each treatment group, and the least squares mean differences (LSMDs) between each dose group and placebo will be reported for Day 43 (Visit 10), along with the corresponding 2-sided 97.5% CIs and p-values.

The study follows a 2-stage group sequential adaptive design using combination test (Lehmacher and Wassmer, 1999) based on the inverse-normal method of combining independent stagewise p-values (Hedges and Olkin, 1985)

The analysis takes into account that the study is a 2-stage group sequential adaptive design assuming equal weighting of each stage, with weights = $1/\sqrt{2}$:

- Stage 1 – Cohort up to the formal IA
- Stage 2 – Cohort post-IA

The following sequential test statistic will be used to test the global null hypothesis at the end of stage 2:

$$T = \sum_{i=1}^2 w_i \phi^{-1}(1 - p_i)$$

Where subscript $i = 1, 2$ represents the stage, p_i represents the appropriate multiplicity adjusted p-value at stage i (for example at stage 1, $p_1 = \min(2 * p_{\min}, 1)$ where p_{\min} is the minimum of the two nominal p-values), the weights $w_{ki} = 1/\sqrt{2}$ satisfy $\sum_{i=1}^2 w_{ki}^2 = 1$ and ϕ^{-1} is the inverse cumulative standard normal distribution function. The test statistic T and $z = \phi^{-1}(1 - p_i)$ have a standard normal distribution, (Lehmacher and Wassmer, 1999).

The combined p-value (2-sided) for the 2 stages, which tests the global null hypothesis, can be calculated by:

$$p = 2 * \{1 - \Phi[\frac{1}{\sqrt{2}} \{\phi^{-1}(1 - p_1) + \phi^{-1}(1 - p_2)\}]\}$$

At the IA one p-value will be computed for each pairwise comparison. Assuming that the trial is not stopped for futility at IA, at the end of the trial the t-test statistics computed at each stage will be used following the p-value combination test method to derive the combined p-value for evaluation of primary efficacy endpoint. Overall statistical significance will be concluded if the combined p-value (2-sided) described above is less than 0.05. For each dose group, statistical significance will be determined in a similar way but using a closed test procedure. Formally, this will be computed as the p-value corresponding to the minimum adjusted Z-statistic of all hypotheses involving the particular dose group being considered. However, if one treatment arm with the largest test statistic is selected for the second stage, the rejection of the global hypothesis implies the rejection of the hypothesis related to the selected hypothesis. The pre-determined alpha value for secondary endpoint testing is specified in [Section 4.6](#).

The analysis will be conducted using SAS and RPACT which also produces the combined effect estimates together with multiplicity adjusted 95% CIs. The stagewise inputs for Rfact will be the model Least squares means, standard errors, sample size per group and degrees of freedom (for estimation of the common standard deviation).

The overall confidence intervals at stage 2 are computed separately for each treatment arm that was selected for stage 2. By use of the Inverse-Normal combination function together with the critical value $Z_{\alpha/2}$, the lower bound of the 2-sided 95% repeated confidence interval for a given treatment arm is found as the smallest value for which the multiplicity-adjusted combination test yields non-rejection at two-sided $\alpha=5\%$. The upper bound of the confidence interval will be found analogously.

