9.4 Planned Efficacy/Outcome Analyses

9.4.1 Analysis of the primary efficacy endpoint

Analysis of the primary efficacy variable will be listed and descriptive statistics will be generated for the observed values and changes from Baseline. Summary outputs will be presented by treatment group and visit.

The formal testing strategy proposed is a flexible combination test based on the inverse normal method (Lehmacher and Wassmer, 1999) with equal weighting of Stage 1 (up to the formal interim analysis) and Stage 2 (post-interim analysis) data. Confirmatory testing of single hypotheses is based on a closed-testing procedure. For the closed testing procedure the Bonferroni approach is used as the intersection test for testing the global and intersection hypotheses. If a dose other than that defined by the "Select the best dose (and any dose with a mean response not worse than 1 point than the selected "best dose")" option (see Section 9.8 for details) is chosen for Stage 2 the adjusted p-value for the chosen dose(s) will be used in the combination test.

The primary efficacy analysis of the study will include the cohort of study participants from Stage 1 (n=) and those who received the selected doses in Stage 2. The primary endpoint, Change from Baseline in MG-ADL, will be analyzed by stage-wise mixed model for repeated measures (MMRM) ANCOVA including a term for Baseline MG-ADL score, region, treatment group, the treatment group by week interaction term, and a term for the stratification factor (categorized as AChR or MuSK). The model will define patient as a random effect and utilize an unstructured covariance pattern. If the model does not converge using the unstructured pattern then an autoregressive covariance structure will be used.

The t-test statistics for each dose group (at each stage) will be used to calculate unadjusted p-values and these will be used to form the p-value combination test(s) as described above. The multiplicity introduced by having potentially 2 doses at the end of the study will be addressed by using a Bonferroni approach. The critical value for this test will be the upper 1.25% percentile of the standard normal distribution (because no alpha will be spent in Stage 1, the futility criterion is not binding and in Stage 2 the alpha is divided between the 2 doses). Similar presentations within each stratification factor may be provided.

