3.9 Changes to protocol-defined analyses

- Mixed model for repeated measures (MMRM) analysis of covariance (ANCOVA) is specified as the model used for the analysis of primary endpoint. In the SAS, MMRM is used as the model only.
- ADDPLAN MC is specified in the protocol for making determinations from the interim analysis. However, SAS or the R package for Adaptive Clinical Trials (RPACT) will be used instead. For the purposes of this analysis, these packages will provide the same functions as ADDPLAN MC.

- The treatment group by week interaction term is specified to be used in the model of analysis of primary efficacy endpoint. In the SAP, treatment group by day interaction will be used instead.
- The Full Analysis Set (FAS) will consist of all study participants in the RS, who have a baseline and at least one post-Baseline MG-ADL measurement. The protocol incorrectly states this as SS.
- Stratification factors used in statistical modeling, such as muscle specific kinase [MuSK(+/-)] and acetylcholine receptor [AChR(+/-)] are defined in the SAP as two binary variables, instead of one binary variable [MuSK(+) or AChR(+)] – this is to account for study participants who may be double-positive.
- Estimands and Intercurrent event handling strategies have been updated based on regulatory feedback.
- Minimal Symptom Expression (MG-ADL score of 0 or 1) at any time up to and include both treatment and observation phase, where the protocol only states to include up to Day 43 (Visit10).
- Potential Hy's Law has been updated to Alanine Aminotransferase (ALT) or Aspartate Aminotransferase (AST) > 3x Upper Limit of Normal (ULN) and total Bilirubin (TBL) > 2x ULN, and Alkaline Phosphatase (ALP) < 2x ULN.
- Calculation of Low-density lipoprotein (LDL) will follow Friedewald equation, where LDL in mmol/L = TC - HDL - TRIG/2.22; LDL in mg/dL = LDL = TC - HDL - TRIG/5 (if all values are in mg/dL). This formula is applicable only if Triglycerides is less than or equal to 400 mg/dL (4.52 mmol/L).
- MG-C responders are defined as at least a 3-point improvement (decrease) from Baseline instead of 5-point improvement.
- Patient Global Impressions of Severity (PGI-S) at each scheduled assessment during the Treatment and Observation Periods instead of change from Baseline of PGI-S.

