4 STATISTICAL/ANALYTICAL ISSUES

4.1 Adjustments for covariates

The efficacy analyses will be adjusted for the following covariates:

- Baseline MG-ADL score,
- Region (North America, Europe, and Asia [excluding Japan], Japan),
- Stratification factors – MG-specific autoantibodies, including muscle specific kinase [MuSK(+/-)] and acetylcholine receptor [AChR(+/-)], both as binary variables.

In statistical modeling, the stratification factors MuSK(+/-) and AChR(+/-) will be based on the values from MG-specific autoantibody assessment at Baseline. In case Baseline MG-specific autoantibody result is missing (and not resolved after data queries), a post-Baseline measurement may be used. If this is not available, then the historical result will be used in the model; if the historical result is missing as well, the stratification factor from IWRS randomization file will be used to determine values used in the model (i.e., if the stratification is MuSK in IWRS, then

MuSK(+/-) will be imputed as positive, otherwise negative; similarly, if stratification factor is AChR in IWRS, then AChR(+/-) will be imputed as positive, otherwise negative).

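### The primary MMRM fits one Baseline MG-ADL slope to all six visits, which costs some Day 43 precision if that slope steepens over time

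*SAP*

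**What the plan says.** SAP 8.2.2 opens the model with "A stage-wise MMRM with treatment group, Baseline MG-ADL score, region", adds the antibody factor(s), and ends the list with "and treatment group by day (interaction term) as fixed factors and study participant as a random effect". It also states "The MMRM will include Days 8, 15, 22, 29, 36 and 43" and "The model will utilize an unstructured covariance pattern for the repeated measures", with an autoregressive fallback.

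No other section supplies a baseline-by-time term:

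- Protocol 9.4.1 describes a model "including a term for Baseline MG-ADL score, region, treatment group, the treatment group by week interaction term" and the stratification factor.
- SAP 3.9 changes only the time unit of the interaction: "treatment group by day interaction will be used instead".
- SAP 4.1 ("The efficacy analyses will be adjusted for the following covariates") lists Baseline MG-ADL, region and the antibody factors, and names no interaction.

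The sensitivity analyses in SAP 8.2.3 use the same MMRM, and SAP 8.3.2 to 8.3.6 send the five continuous secondary endpoints to 8.2.2. The trimmed-mean analysis in SAP 8.2.4.1 differs: it takes its baseline coefficient from an ANCOVA of Day 43 alone.

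**The concern.** The model gives treatment its own effect at each day but holds the baseline slope equal at all six. There are reasons to doubt that the slope is constant. MG-ADL cannot fall below 0 (Protocol 8.1.4.1) and entry requires at least 3 (inclusion criterion 5a), so a participant entering at 3 can improve by 3 points at most, while one entering at 12 has room for 12. Protocol 4.2 reports that in the Phase 2 study the greatest reductions came after six infusions. A bounded score with accumulating improvement would tend to tie change more strongly to baseline at Day 43 than at Day 8.

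If so, an unstructured fit with less variable early visits pulls the common slope towards those visits and leaves baseline variance in the Day 43 contrast. The same model supplies the stage-wise p-values and the SD used for sample size re-estimation. Table 2-1 power is as low as 0.632 with both doses at 1.5 points and SD 4, so precision that needs no extra enrolment is worth having.

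**Working it through.** **1. The plan's own figure.** The SAP 2.4 design was simulated with 100,000 runs per scenario: 30 per arm in Stage 1, futility at one-sided p > 0.5, dose selection within 1 point, the Stage 2 formula held to 30 to 50 per arm, and a closed Bonferroni test with the inverse-normal combination at one-sided 0.025. Table 2-1 reproduces:

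- 0.752 against 0.750 stated (1.5/1.5, SD 3.5)
- 0.631 against 0.632 (1.5/1.5, SD 4)
- 0.797 against 0.792 (1.5/2.0, SD 4)

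All 14 powers agree within 1 point. They depend on an effect and an SD only, not on any baseline slope.

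**2. Formula.** Let b_t be the true slope of change on baseline at visit t, S the residual covariance, s43 the residual SD at Day 43 and V the baseline variance. With complete data the fitted common slope tends to b = 1'S⁻¹b_t / 1'S⁻¹1. The Day 43 contrast then has variance proportional to s43² + (b43 − b)²V, against s43² with a visit-specific slope. The relative loss is

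L = (b43 − b)² V / s43².

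**3. Inputs.** From the documents: SD 3.5 to 4 and 30 per arm in Stage 1 (SAP 2.4), and six visits (SAP 8.2.2). Not in the documents, so assumed:

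- baseline SD 2.5 to 3.5
- slopes changing linearly, from −0.10 to −0.20 at Day 8 to −0.20 to −0.50 at Day 43
- adjacent-visit correlation 0.70 to 0.85, decaying with lag
- Day 8 SD 60% to 100% of the Day 43 SD

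**4. Large-sample results (s43 = 3.5, baseline SD 3, so V / s43² = 9 / 12.25).**

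| Slope, Day 8 to Day 43 | b, equal visit SDs | L | b, Day 8 SD 60%, correlation 0.85 | L |
|---|---|---|---|---|
| −0.20 to −0.20 | −0.20 | 0% | −0.20 | 0% |
| −0.15 to −0.35 | −0.25 | 0.7% | −0.173 | 2.3% |
| −0.10 to −0.40 | −0.25 | 1.7% | −0.135 | 5.2% |
| −0.10 to −0.50 | −0.30 | 2.9% | −0.147 | 9.2% |

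Third row, right: (0.40 − 0.135)² × 9 / 12.25 = 0.0702 × 0.735 = 5.2%. Extreme corner (last row with baseline SD 3.5): (0.50 − 0.147)² × 12.25 / 12.25 = 12.5%.

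**5. Check at 30 per arm.** Both models were fitted to 6,000 simulated Stage 1 datasets per setting, with Day 8 SD 60%, correlation 0.85 and, except in the last line, baseline SD 3:

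- Equal slopes: −0.6% (the single slope is marginally better)
- −0.15 to −0.35, SD 3.5: 0.8%
- −0.10 to −0.40, SD 3.5: (0.9220 / 0.9027)² − 1 = 4.3%
- −0.10 to −0.40, SD 4: 3.1%
- −0.10 to −0.50, SD 3.5, baseline SD 3.5: 12.1%

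The mean contrast was unbiased under both models in every setting.

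**6. Power.** Treat the planned SD as that of the single-slope model, and replace it with SD / √(1 + L). At L = 4%, 3.5 becomes 3.5 / √1.04 = 3.43.

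| Effects, SD | As planned | L = 4% recovered | L = 10% recovered |
|---|---|---|---|
| 1.5/1.5, 3.5 | 0.753 | 0.771 | 0.794 |
| 1.5/1.5, 4 | 0.631 | 0.648 | 0.676 |
| 1.5/2.0, 4 | 0.796 | 0.814 | not run |

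**7. Missing scores.** A separate large-sample check used 60,000 per arm, baseline SD 3, correlation 0.8 and less variable early visits. The three steepening patterns gave losses of 1.8%, 4.2% and 7.1%. With about 9% to 11% of scores missing after rescue these became 2.2%, 4.9% and 8.2%. The Day 43 estimates from the two models differed by at most about 0.015 points.

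**The case against.** The strongest reply is that the documents do not show unequal slopes. The familiar rule that the slope of change equals the correlation with baseline minus 1 needs equal variances at baseline and follow-up, and the eligibility floors on MG-ADL and QMG make that uncertain. Less variable early visits are also an assumption. This stands, and it makes the point conditional.

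The trimmed-mean analysis already adjusts with a Day 43 coefficient, for the primary and all five continuous secondary endpoints. That is true, but it is supplementary, uses a composite strategy, and leaves the primary test unchanged.

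A larger model SD would raise the Stage 2 sample size towards the 90% conditional power target, up to the cap. This partly offsets the loss, but it pays for it in participants.

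A reader might also infer that interim decisions are distorted. SAP 4.4.1 selects doses on mean responses within 1 point, and futility at p > 0.5 amounts to the sign of the estimate. Neither rule uses the standard error, and no effect on either has been quantified. Nor is it shown that the model mis-extrapolates scores set to missing after rescue. An unstructured MMRM also conditions on each participant's observed post-baseline scores, and the difference in step 7 is negligible.

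**Conclusion.** The concern holds as a conditional efficiency point. The plan shares one baseline slope across six visits and tests only the last. If the slope steepens, Day 43 is under-adjusted. The likely cost is about 1% to 5% of the Day 43 contrast variance, equal to 0.3 to 1.5 participants per arm of 30 (0.01 × 30 to 0.05 × 30). It is zero with equal slopes. It reaches about 10% or more only when a large slope change, high correlation, quiet early visits and a wide baseline spread coincide.

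These sizes rest on assumed slopes, SDs and correlations. The direction follows from the model's structure once the slope steepens and the early visits are no more variable than Day 43.

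It would be wrong to conclude that precision is certainly lost, that the treatment effect is biased, that type I error is at risk, or that Table 2-1 is in error on this account. The documents give no per-visit slopes, the contrast was unbiased under both models with complete data, and the stated powers reproduce without any assumption about baseline slopes.

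**What to change.** In SAP 8.2.2, add baseline score by day as a fixed effect in the stage-wise MMRM, in identical form for Stage 1 and Stage 2, so that the combined p-values and estimates come from the same model. Record the addition in SAP 3.9, as was done for the change from week to day, and align Protocol 9.4.1. Make the choice blind to treatment-level data.

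Carry the term to the continuous secondary endpoints at their own scheduled visits. In the Protocol 1.3 schedule, MG-C and QMG have the same six treatment-period visits as MG-ADL. The MG Symptoms PRO scales have four (Visits 4, 5, 8 and 10), and the loss for those scales has not been sized.

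The cost is a short text and code change. It adds 6 − 1 = 5 fixed-effect parameters per stage for a six-visit endpoint and 4 − 1 = 3 for the PRO scales. If the slopes are in fact equal, the price is about 0.6% more variance at 30 per arm.

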4.6 Multiple comparisons/multiplicity

The statistical analysis of the primary efficacy and selected secondary efficacy endpoints will account for multiplicity and control the familywise type I error rate at a 2-sided alpha level of 0.05 by using a parallel gatekeeping testing procedure with a truncated Hochberg test for each of the 6 type I error families (corresponding to the primary endpoint and the five secondary endpoints).

The hypotheses are mapped into 2 sets so that hypotheses within each set correspond to the same rozanolixizumab dose.

Serial restrictions are applied so that the endpoints can only be tested for each dose, if all previous endpoints for that dose are significant.

For family 1, (the primary endpoint hypotheses corresponding to the pairwise comparisons of each dose versus placebo) the Hochberg truncation parameter is set to 0 which is equivalent to using the Bonferroni approach, where the type I error will be split equally between dose level rozanolixizumab [REDACTED] so that each dose level will be tested at a 2-sided alpha level of 0.025. Whereas, for families 2-5 the Hochberg truncation parameter is set to 0.2, and for the final family the truncation parameter is 1, so that the standard Hochberg test is used.

The scenarios for the sequential procedure are described below and begins with the evaluation of the primary efficacy endpoint.

Scenario 1: One of the two doses of rozanolixizumab is statistically significant for the primary endpoint:

1. Test rozanolixizumab vs placebo for change from Baseline to Day 43 in MG-C score at a 2-sided alpha level of 0.025. If significant in favor of rozanolixizumab, then proceed to step 2. Otherwise, the testing procedure is concluded.
2. Test rozanolixizumab vs placebo for change from Baseline to Day 43 in QMG score at a 2-sided alpha level of 0.025. If significant in favor of rozanolixizumab, then proceed to step 3. Otherwise, the testing procedure is concluded.
3. Test rozanolixizumab vs placebo for change from Baseline to Day 43 in MG Symptoms PRO 'Muscle Weakness Fatigability' score at a 2-sided alpha level of 0.025. If significant in favor of rozanolixizumab, then proceed to step 4. Otherwise, the testing procedure is concluded.

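### SAP 8.2.2 decides each dose on the primary endpoint by a closed test at two-sided 0.05, SAP 4.6 tests the same hypotheses at 0.025 each, and the two rules can give opposite verdicts

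*SAP*

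**What the plan says.** SAP 8.2.2 combines the stagewise p-values with equal weights by the inverse-normal method. For the global null hypothesis, the input at each stage "represents the appropriate multiplicity adjusted p-value at stage" i; at Stage 1 that is twice the smaller of the two nominal p-values, capped at 1. On the result: "Overall statistical significance will be concluded if the combined p-value (2-sided) described above is less than 0.05". On the individual doses: "For each dose group, statistical significance will be determined in a similar way but using a closed test procedure". The dose-level p-value comes from the smallest adjusted Z among the hypotheses that involve that dose. The overall 95% interval for each dose follows the same logic, since its lower bound "is found as the smallest value for which the multiplicity-adjusted combination test yields non-rejection at two-sided" 5%. Section 8.2.2 sends the reader to 4.6 for one purpose only: "The pre-determined alpha value for secondary endpoint testing is specified in" that section.

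SAP 4.6 also covers the primary endpoint. It is family 1, where "the Hochberg truncation parameter is set to 0 which is equivalent to using the Bonferroni approach", "so that each dose level will be tested at a 2-sided alpha level of 0.025". The result selects the route for the secondary endpoints; Scenario 1, for example, is "One of the two doses of rozanolixizumab is statistically significant for the primary endpoint". A closing note says that the p-values follow the inverse-normal approach used for the primary endpoint, without saying whether they are closed-test adjusted.

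Protocol 9.4.1 specifies a closed test with a Bonferroni intersection test. It also specifies combination tests built from unadjusted p-values, with a critical value that cuts off the upper 1.25% of the standard normal distribution. SAP 3.1 refers to 4.6 for the levels of the multiple testing procedure. SAP 3.9, which lists departures from the protocol, does not mention the point.

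**The concern.** A closed test with a Bonferroni intersection is not plain Bonferroni. Once the intersection is rejected, a dose needs only its own combined p below 0.05; plain Bonferroni always asks for 0.025. Three readings are open:

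- **(a)** closed-test p-value against 0.05, as in 8.2.2;
- **(b)** closed-test p-value against 0.025, the literal combination of 8.2.2 and 4.6, which corrects twice;
- **(c)** the dose's own unadjusted combined p-value against 0.025, as in 4.6 and the protocol's 1.25% critical value.

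At stake is the criterion for a dose-level claim in a two-dose Phase 3 trial, and through it the choice between Scenario 1 and Scenario 2. If the rule is still open when the data are unblinded, choosing the rule can mean choosing the verdict.

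**Working it through.** **Inputs.** From SAP 2.4, 4.4.1 and 8.2.2: stage weights 1/√2; 30 per arm in Stage 1 and 30 to 50 in Stage 2; conditional power target 0.9; SD 3.5 or 4; futility at one-sided p > 0.5; the second dose kept if within 1 point of the best. Critical values are 1.960 for two-sided 0.05 and 2.2414 for two-sided 0.025.

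**Formula.** Z = [z(1−p₁) + z(1−p₂)]/√2, and two-sided p = 2[1−Φ(Z)]. For the intersection, each stagewise p is min(2·p_min, 1) when both doses are tested.

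**Example 1, both doses continue.** One-sided p-values: dose A 0.01 then 0.01; dose B 0.06 then 0.10.

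- Intersection (0.02 at each stage): (2.054 + 2.054)/√2 = 2.904, p = 0.0037.
- Dose B alone: (1.555 + 1.282)/√2 = 2.006, p = 0.0449.
- The closed-test p for dose B is the larger of the two, 0.0449. It wins under (a) and loses under (b) and (c).
- The data are plausible under the selection rule. With 87 df, the Stage 1 t-quantiles are 2.370 and 1.570, a difference of 0.800. Multiplied by SD·√(2/30), this is a gap between doses of 0.72 points at SD 3.5 and 0.83 at SD 4, inside the 1-point margin.

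**Example 2, only the better dose continues.** Its one-sided p-values are 0.10 then 0.028.

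- Closed: Stage 1 becomes 0.20, so (0.842 + 1.911)/√2 = 1.946, p = 0.0516. It loses under (a).
- Unadjusted: (1.282 + 1.911)/√2 = 2.258, p = 0.0240. It wins under (c).

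**Which rule lies behind Table 2-1?** The design was simulated with 400,000 trials per scenario, taking power as at least one dose rejected. Normal approximation, known SD:

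| Scenario | Table 2-1 | (a) | (c) | (b) | (a) and (c) differ on a dose |
|---|---|---|---|---|---|
| 1 (null) | 0.020 | 0.0198 | 0.0229 | 0.0102 | 0.9% |
| 2 | 0.400 | 0.4105 | 0.4492 | 0.3060 | 12.4% |
| 4 | 0.750 | 0.7623 | 0.7948 | 0.6656 | 13.5% |
| 5 | 0.864 | 0.8721 | 0.8949 | 0.8070 | 9.3% |
| 7 | 0.943 | 0.9488 | 0.9602 | 0.9103 | 6.7% |
| 14 | 0.871 | 0.8790 | 0.8993 | 0.8102 | 9.6% |

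With pooled-SD t-tests in place of the normal approximation:

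- (a) is within 0.7 points of the stated power in all 12 non-null scenarios (scenario 4: 0.753 against 0.750).
- (b) is 3.9 to 11.4 points below the table, or 3.3 to 10.4 if the re-estimation also uses 2.2414.
- (c) is 1.2 to 4.8 points above the table for any dose, and 3.6 to 8.6 points below (a) for both doses. These ranges cover re-estimation as written and re-estimation aligned with 2.2414.
- (a) and (c) disagree on at least one dose in 6.9% to 13.7% of non-null trials, and on whether any dose wins in 2.2% to 7.5%. (a) and (b) disagree on a dose in 8.1% to 15.8%.

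**Mixing the rules.** With truncation parameter 0, family 1 leaves 0.025 to pass on when one dose wins. A closed test at 0.05 uses the whole level. If (a) is the gate and 4.6 is otherwise unchanged, the worst case (one dose truly effective, the other null, MG-C null, independence) has one-sided error 1 − 0.975 × 0.9875 = 3.72%, against 2.5%. Simulation with both doses forced on, 1,000,000 trials per case and effect 2 to 3, gives 3.5% to 3.7% with unadjusted MG-C p-values and 2.9% to 3.0% with adjusted ones. Under the SAP's own selection rule, for effects 1 to 2, the figures are 1.9% to 2.6% and 1.5% to 2.1%.

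**The case against.** The best defence is that the documents lean towards 0.025 per dose. SAP 3.1 points to 4.6 for multiple-testing levels, 4.6 names the primary endpoint, the protocol gives the 1.25% critical value, and the stagewise intervals in 8.2.2 are 97.5%. Section 8.2.2 writes 0.05 only for the global test and never states a per-dose level. On this view (b) has little support, SAP 2.4 could describe a plain Bonferroni split, and Table 2-1 is planning evidence rather than a decision rule. Either rule also controls error on the primary endpoint.

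Part of this stands. The per-dose 0.05 is an inference, SAP 2.4 does not name a closed test, and Table 2-1 does not say whether power means any dose or both. But the inference is firm: the dose rule follows directly on the 0.05 global rule, and the per-dose interval is inverted at 5%. In Example 1, that 95% interval would exclude zero for a dose that 4.6 calls non-significant. Reading (b) has textual support too, because 8.2.2 defines the dose-level p-value from adjusted Z-statistics and 4.6 takes its p-values from there. Precedence is not settled, since 8.2.2 cites 4.6 only for secondary endpoints.

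**Conclusion.** The concern holds and must be fixed before unblinding. The plan gives two confirmatory rules for the same two hypotheses. They give different verdicts on at least one dose in roughly 7% to 14% of simulated non-null trials when (a) is compared with (c), and the power table belongs to only one of them. The case does not rest on error inflation: each rule alone controls the primary endpoint, and familywise error under the SAP's own selection rule is close to or below nominal.

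The figures assume normally distributed data, no missing values, the SAP's selection rule applied without IDMC discretion, and power defined as any dose rejected. The familywise-error runs also assume SD 3.5 and endpoint correlations of 0, 0.3 and 0.6.

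**What to change.** State one dose-level rule for the primary endpoint, name the combined p-value used in every family of 4.6, and align SAP 8.2.2, SAP 4.6 and Protocol 9.4.1. Two options are coherent.

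1. **0.025 per dose.** Use unadjusted per-dose combined p-values at two-sided 0.025 (critical value 2.2414) for the primary endpoint, unadjusted combined p-values throughout 4.6, and overall intervals at 97.5% per dose. Change the SAP 2.4 re-estimation to 2.2414 on the unadjusted Stage 1 p-value, without halving the conditional error, and re-run Table 2-1. Against the closed test this costs 3.9 to 8.6 points of both-dose power (scenario 7: 0.643 to 0.587; scenario 4: 0.439 to 0.353). Any-dose power rises by 0.9 to 3.8 points and average sample size falls by 1.3 to 2.8. Simulated one-sided familywise error is at most 2.47%.
2. **Closed test at 0.05.** Keep the 95% intervals, SAP 2.4 and Table 2-1, and change what 4.6 passes on when only one dose wins. The simplest form passes nothing unless both doses win. Its price is no confirmatory secondary claim when exactly one dose wins, which is 20% to 63% of non-null trials (63% in scenario 5) and includes trials where the interim dropped a dose. Simulated one-sided familywise error is at most 2.52%, within simulation error of 2.5% (standard error 0.016 points). A less costly form is a single closed or graphical procedure over all 12 hypotheses.

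Both need SAP and protocol wording; option 1 also needs the SAP 2.4 formula changed and the simulation re-run. Neither needs more participants. If a secondary claim for a single winning dose matters, option 1 is the simpler route.
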